5 TRIAL PROCEDURES

5.1 Recruitment

Patients will be recruited to Part A of the study through the Phase 1 units at RMH, Sutton and Christie Hospital, Manchester. Recruitment to Part B will be coordinated by the melanoma units of each site. The assignment of a patient to a particular cohort will be coordinated by RM-CTU.

5.2 Informed consent

The patient must personally sign and date the latest approved version of the informed consent form before any trial specific procedures are performed, and between Day -28 and the first dose of CCT3833. Informed consent will allow registration into the screening stage of the trial, during which evaluations will determine eligibility. Following confirmation of eligibility, patients will proceed to trial entry.

Written versions of the participant information and informed consent will be discussed with the participants.

It will be clearly stated that the participant is free to withdraw from the trial at any time, for any reason, without prejudice to future care and with no obligation to give the reason for withdrawal. The patient will be allowed as much time as wished to consider the information, and the opportunity to question the Investigator or other independent parties to decide whether they will participate in the trial. As a minimum, the patient may consent after considering the information for no less than 1 day.

Written informed consent will be obtained by means of patient dated signature, and dated signature of the person who presented and obtained informed consent; the dates should be the same. The person obtaining consent must be suitably qualified and experienced, and have been delegated the responsibility to do so by the Chief Investigator/Principal Investigator (as evidenced by signing the trial delegation log). A copy of the signed informed consent will be given to the patient. The original signed form and information sheet must be retained in the Investigator trial file at the trial site.

5.3 Screening and eligibility assessment

At enrolment, each potential patient will provide informed consent prior to starting any study specific procedures. Each potential patient is assigned a unique patient identifier. If a patient withdraws from the study, then the identifier cannot be reused.

Demographic data and other characteristics will be recorded and will include: date of birth, gender, race and ethnicity according to local regulations. A standard medical, and

medication and surgical history will be obtained, along with review of the selection criteria with the patient.

Each patient will undergo Screening during the 28 days prior to admission, to confirm eligibility. Tumour assessments and other clinical data obtained as standard of care prior to consent may be used for the study, provided the assessments fall within the protocol-specified period prior to the first dose of study treatment.

5.4 Randomisation and blinding

No randomisation will be performed for this trial. This is an open-label trial, therefore no blinding is necessary.

5.5 Patient evaluability

All patients who meet the eligibility criteria and receive at least one administration of CCT3833 will be evaluable for safety.

Patients who receive less than 75% of the planned doses of CCT3833 during the first treatment cycle (for reasons other than toxicity) will not be evaluable for dose review decisions. Patients who are not evaluable may be replaced.

All patients who meet the eligibility criteria, receive at least 75% of the planned doses of CCT3833 in the first treatment cycle, and have a baseline assessment of disease will be evaluable for disease response according to the RECIST criteria v1.1 (Appendix 5). To be assigned a status of complete response (CR) or partial response (PR), changes in tumour measurement must be confirmed by repeat measurements performed no less than 4 weeks after the response criteria are met. To be assigned a status of stable disease (SD), follow-up measurements must have met the SD criteria at least once, and at least 6 weeks after the first dose of CCT3833 has been taken.

6 TREATMENT

6.1 Definition of treatment cycle

The first dose of continuous dosing defines Cycle 1 Day 1. All treatment cycles have a duration of 28 days. There will be no delays between cycles, i.e. Day 29 represents Cycle 2, Day 1.

6.2 Selection of the Phase 1 starting dose

The starting dose of CCT3833 is 20 mg, taken as two 10 mg capsules. The starting schedule is a once daily continuous dosing schedule, but other dosing regimens may be considered depending on tolerability and exposures.

6.3 Treatment schedule

CCT3833 has been formulated into 5 mg, 10 mg, 25 mg or 75mg hydroxy-propyl-methyl-cellulose (HPMC) capsules. A combination of these capsules will be combined to provide the appropriate daily dose.

A single dose will be given between Days -7 and -3 prior to commencing continuous dosing; this will be for clinical safety and pharmacokinetic assessment purposes.

The pharmacokinetics of the first dose in the first subject will be analysed with a rapid turnaround time before further patients are dosed. For the first dose administration at all dose escalation levels, patients will be admitted to (or required to stay close to) the clinical research facility for a period of 48 hours, for blood PK and ECG assessments, and to allow close observation of potential side effects. Vital signs including temperature, pulse rate and BP will also be assessed. The results of the bioanalysis of the pharmacokinetic sampling will not be required before commencement of the first continuously dosed escalation cohort the following week.

CCT3833 will then be taken continuously according to a daily schedule. The treatment schedule will be reviewed as the trial progresses and the dosing schedule may be amended during the course of the trial. If evidence of dose-limiting toxicities (DLTs) occur in early cohorts of dose escalation (or other emerging pharmacokinetic and/or pharmacodynamic data suggest it to be appropriate), the dosing schedule may be altered from once-daily dosing. For example, the single daily dose may be split into two (or more) daily doses to investigate whether a higher total daily dose could be delivered whilst avoiding DLTs. Similarly, a decision to explore intermittent dosing (for example, 2 weeks of continuous treatment followed by a 1 week break) may be made if the real-time monitoring of patients indicates this to be appropriate.

6.4 Definition of dose-limiting toxicity

The dose-limiting toxicity (DLT) is defined using the National Cancer Institute's (NCI) Common Terminology Criteria for Adverse Events (CTCAE) version 4.03 (Appendix 4). DLTs identified in Cycle 1 of treatment will inform the decision to dose escalate through the increasing dose levels. Significant toxicities and DLTs in later cycles will be considered throughout the treatment period and in determining the recommended Phase 2 dose.

A DLT is defined as a probably or highly probably drug related toxicity as detailed in Table 8.

Table 8: Dose-limiting toxicity definitions and criteria

Toxicity	Criteria
Any toxicity causing a decrease in treatment dose intensity	Inability to deliver > 75% of the planned dose intensity in a cycle due to CCT3833-related toxicity
Haematology	
 • Grade 4 neutropenia for > 1 week • Grade 4 thrombocytopenia or grade 3 thrombocytopenia with bleeding • Febrile neutropenia • Grade 4 anaemia (unless a specific cause of blood loss is identified)
Cardiovascular	
 • Any grade 3 or above • Hypertension (grade 3 or above) lasting more than 2 weeks despite optimal treatment
Skin	Any grade 3 or above, persisting for > 7 days despite optimal treatment
Metabolic	Grade 3 or above hyperglycaemia (measured in the fasted state)
Any other drug related G3/4 toxicity except:	
 • Alopecia • Nausea that is sub optimally managed • Vomiting that is sub optimally managed • Diarrhoea that is sub optimally managed • Constipation that is sub optimally managed
Any other toxicity that is considered dose-limiting in the view of the Investigator	

Baseline laboratory values are those reported before the first dose of CCT3833.

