6.6 Dose escalation scheme

Patients will be enrolled to ensure a minimum of 3 and a maximum of 6 evaluable patients per cohort. The dose level of CCT3833 will be assigned using all available data by the Sponsor in conjunction with the Safety Review Committee (SRC). Dose assignment will be made after considering the number of patients already enrolled at the current dose level, the number of DLTs (and any other drug related AEs) observed at the current dose level, and the number of patients enrolled who are at risk of developing a DLT.

The first patient in all cohorts will be treated for 7 days taken from Day 1, before the second and third patients can take their first dose of CCT3833 in parallel. Patients who receive less than 75 % of their planned doses in Cycle 1, taken from Day 1 onwards, for reasons other than toxicity will not be evaluable for assessment of DLT for dose review decisions and will be replaced in the cohort.

In order to make the decision to escalate the CCT3833 dose, three evaluable patients must have completed one cycle of treatment (28 days). The time between cohorts is therefore approximately 6 weeks.

The dose increases between cohorts will be up to 100%, i.e. doubling of the dose (dosed on a flat scale and not by body weight or body surface area), until a probable or highly probable drug-related CTCAE v4.03 (Appendix 4) Grade 3 AE (or grade 4 haematological toxicity) is reported. Subsequent dose increases between cohorts will be driven by reported safety data and available PK and PD data. The available PK data for all patients will be reviewed as part of the dose escalation data. PK data for a minimum of two patients in the current cohort will be required to inform dose review decisions. PK data for a minimum of two patients from the previous cohort will also be required.

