6.7.2 Safety review committee

Specific dose escalation meetings will be conducted every 4-6 weeks, or when 3 patients have completed the 28-day DLT window, whichever is earlier. These will be to determine if the dose level has been tolerated by the patients and that it is safe to escalate the dose to the next level. Dose escalation decisions will be led by the SRC which will consist of:

- Chief Investigator or delegate
- Principal Investigator or delegate from each investigational site

- RM CTU operations manager or delegate
- Trial Statistician
- Senior Phase 1 trial clinician (who is not CI/PI)
- Senior melanoma trial clinician (who is not CI/PI)
- Chairperson (must be independent of the Investigators/institution)

Further internal or external experts may be included by the SRC as necessary.

Part B, the dose expansion stage, is being conducted in two large and experienced melanoma units who have also worked extensively together on trials on multiple previous occasions. The above described SRC will also convene at regular intervals (at least quarterly) to review the accumulating safety data from the trial during the dose expansion stage; more frequent meetings will be dictated by availability and severity of on-going safety information. They will meet (teleconference) within a week of any grade 4 toxicities or death, regardless of whether thought attributable to CCT3833 or not.

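### A patient who has already had a DLT can be declared non-evaluable and replaced, and the protocol does not settle whether a DLT after the run-in dose enters the escalation count

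*Combined protocol and SAP*

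**What the plan says.** Section 6.4 ties escalation to one cycle: "DLTs identified in Cycle 1 of treatment will inform the decision to dose escalate through the increasing dose levels". It adds: "Significant toxicities and DLTs in later cycles will be considered throughout the treatment period and in determining the recommended Phase 2 dose".

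On when that cycle starts, section 6.1 states: "The first dose of continuous dosing defines Cycle 1 Day 1". Section 6.7.2 calls a meeting "when 3 patients have completed the 28-day DLT window". Each Part A patient has had the drug before then, because section 6.3 provides: "A single dose will be given between Days -7 and -3 prior to commencing continuous dosing; this will be for clinical safety". Section 1.2.1, however, describes this single dose and its washout as belonging to the first cycle.

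On who counts, section 6.6 says that patients taking under 75% of Cycle 1 doses, counted from Day 1, "for reasons other than toxicity will not be evaluable for assessment of DLT for dose review decisions and will be replaced in the cohort". Section 5.5 has the same threshold and says such patients may be replaced. Section 6.13 also allows replacement for withdrawal before the end of Cycle 1 unrelated to drug toxicity, whatever share of doses was taken. None of the three mentions a patient who has already had a DLT.

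The decision rules are in sections 6.5 and 6.8. With no DLT in three patients, escalation can be considered. One in three expands the cohort to six. Two at a level make it non-tolerated. Neither section states a time window. In Table 8 the residual row reads "Any other drug related G3/4 toxicity except", whereas the cardiovascular, skin and hyperglycaemia rows cover Grade 3 and above.

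**The concern.** The escalation rule turns on whether the count is 0, 1 or 2, so a single event that is in or out of the tally changes the decision. The same count defines the MTD, which is a primary endpoint in section 3.1.

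The evaluability rule is meant to remove patients who were too lightly exposed to be informative about the absence of a DLT. A patient who has had a DLT is informative whatever happens afterwards. As written, the rule removes both kinds. In advanced cancer, a DLT followed by progression within the same 28 days is a plausible sequence.

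The run-in dose is each patient's first exposure and is given partly to assess safety. A qualifying toxicity that arises after it and settles before Day 1 is, under sections 6.1 and 6.4, in neither Cycle 1 nor a later cycle. Two readers could therefore report different counts from the same cohort.

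**Working it through.** **Plan's own figures.** Section 10.2 gives no formal sample-size calculation, and no target DLT rate or escalation probability is stated. The enrolment totals reproduce (3 × 9 = 27; 42 + 27 = 69) but do not bear on this point.

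**Effect on the count (no assumptions needed).** Let one DLT patient take under 75% of doses (fewer than 21 of 28) for another reason and be replaced.

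- 1 DLT in 4 treated: 1 − 1 = 0 DLTs in 4 − 1 = 3 evaluable. Reads as 0/3, escalation can be considered. With the DLT counted, the cohort expands.
- 2 DLTs in 4 treated: reads as 1/3, expand. With both counted, the level is non-tolerated.
- 2 DLTs in 7 treated: reads as 1/6, which meets the MTD definition in section 3.1. With both counted, it does not.

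**Illustrated effect on escalation.** For a counted DLT rate r, the chance of clearing a level (0/3, or 1/3 then 0/3) is

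E(r) = (1−r)³ + 3r(1−r)² × (1−r)³.

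At r = 0.30: 0.343 + 0.441 × 0.343 = 0.494.

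Let p be the true rate, d the share of DLT patients lost for non-toxicity reasons and w the share of non-DLT patients so lost. All three are assumed.

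- As written: r = p(1−d) / [p(1−d) + (1−p)(1−w)]
- DLT patients kept: r = p / [p + (1−p)(1−w)]

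For p = 0.30 and d = w = 0.20, as written r = 0.24/(0.24 + 0.56) = 0.300; kept, r = 0.30/(0.30 + 0.56) = 0.349. For d = 0.20 and w = 0, as written r = 0.24/(0.24 + 0.70) = 0.255; kept, r = 0.300.

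| p | d | w | E as written | E with DLT patients kept |
|---|---|---|---|---|
| 0.30 | 0.10 | 0.10 | 0.494 | 0.449 |
| 0.30 | 0.20 | 0.20 | 0.494 | 0.399 |
| 0.30 | 0.10 | 0 | 0.539 | 0.494 |
| 0.30 | 0.20 | 0 | 0.588 | 0.494 |
| 0.50 | 0.20 | 0.20 | 0.172 | 0.117 |
| 0.50 | 0.20 | 0 | 0.242 | 0.172 |

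Where loss is unrelated to DLT (d = w), the written rule leaves the counted rate at p. It lowers the rate only where loss is commoner among DLT patients.

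**Run-in events.** If a share m of DLTs falls outside the window, the counted rate is p(1−m). At p = 0.40, E is 0.309 with m = 0, 0.378 with m = 0.10 and 0.454 with m = 0.20. The documents give no value for m.

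**Events pending at Day 28.** With onset on day k counted as the first day, 28 − k + 1 days have elapsed by Day 28. A criterion of more than 7 days (skin, Grade 4 neutropenia) needs k ≤ 21; one of more than 14 days (hypertension) needs k ≤ 14. The text gives no status to an event that began later and is unresolved when the committee meets.

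**Grade 5.** Table 8's first row makes it a DLT if more than 75% of planned intensity cannot be delivered because of drug toxicity. A drug-related death by about Day 21 leaves at most 21/28 = 75% and so meets that row. The residue is a later death in Cycle 1 that meets no other named row; it is a DLT only through the investigator-judgement row.

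**The case against.** The strongest reply is that events left out of the tally are not unseen. The committee reviews all adverse events (section 6.8), and dose assignment must weigh other drug-related events and patients still at risk of a DLT (section 6.6). Section 6.5 counts patients who experience a DLT and section 6.8 counts DLTs observed at the level, so a literal reader could include the discarded patient, a run-in event or a late one. All of this stands. It shows, however, that sections 6.5 and 6.8 give one count and sections 6.4 and 6.6 another; discretion does not say which is the formal count.

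A reader might infer more than the text supports, in three ways.

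- **That late-onset and fatal DLTs are simply missed.** Section 6.4 says later-cycle DLTs will be considered, and section 6.9.1 says a DLT can occur in any cycle. The first patient starts at least 7 days ahead and so is past Day 28 when the third completes. Most fatal events are caught by the dose-intensity row or the rows for Grade 3 and above.
- **That every gap biases the DLT rate downwards.** For the evaluability rule this is so only if loss is linked to having a DLT, as the table shows.
- **That a lost DLT leads to a doubled dose.** Under section 6.6 the allowance of up to 100% ends once a probable or highly probable drug-related Grade 3 event, or Grade 4 haematological toxicity, is reported. That condition carries no window or evaluability test, and 0/3 only permits escalation to be considered.

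**Conclusion.** Two points hold. First, the evaluability and replacement rules have no exception for a patient who has already had a DLT, so one DLT in four treated patients can be read as 0/3. That follows from the wording and needs no assumed rate. Second, the sections contradict one another on whether a DLT after the run-in dose counts. Two smaller ambiguities go with these: duration-based events still open at Day 28, and a fatal event that meets no named row of Table 8.

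How often this would change a decision cannot be estimated from the documents. The probabilities rest on assumed DLT rates of 30% to 50% and assumed losses or uncounted shares of 10% to 20%. They show that the effect of the replacement rule runs from no distortion (0.494 either side of an unrelated 20% loss) to 0.588 against 0.494 when only DLT patients are lost. A conclusion that the design systematically understates toxicity would go beyond the text.

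**What to change.** State in sections 5.5, 6.6 and 6.13 that a patient with a DLT stays evaluable in the DLT count whatever share of planned doses was taken.

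Reconcile sections 1.2.1, 6.1, 6.4, 6.5, 6.7.2 and 6.8 so that toxicity after the run-in dose, and events whose duration criterion is still open at Day 28, each have one stated status in the tally. Reconcile the two grade wordings in Table 8 so that a fatal event meeting no other row also has a stated status. The choice among these readings is for the sponsor and the safety review committee; what is needed is that one is written down.

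The cost is amendment wording and a somewhat more conservative count. If loss is unrelated to DLT, keeping DLT patients while replacing the others raises the counted rate above the true one (0.349 against an assumed 0.30 with 20% loss), and the chance of escalating falls from 0.494 to 0.399. If the sponsor chooses to wait for an open duration criterion, some decisions would be delayed by one to two weeks.

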6.5 Definition of maximum tolerated dose

Part A of the trial aims to define the MTD of CCT3833.

A minimum of 6 evaluable patients is necessary to determine the MTD. A dose will be considered non-tolerated and dose escalation will cease if 2 or more patients experience a DLT at a dose level. Once the non-tolerated dose is defined, the MTD will be confirmed at the previous dose-level below the non-tolerated dose; a dose between the non-tolerated dose and the last tolerated dose may also be investigated. The recommended Phase 2 dose (RP2D) will be defined as either the MTD, or the highest dose that is tolerated and has demonstrated efficacy. The dose will be determined following discussion of all relevant study data.

6.6 Dose escalation scheme

Patients will be enrolled to ensure a minimum of 3 and a maximum of 6 evaluable patients per cohort. The dose level of CCT3833 will be assigned using all available data by the Sponsor in conjunction with the Safety Review Committee (SRC). Dose assignment will be made after considering the number of patients already enrolled at the current dose level, the number of DLTs (and any other drug related AEs) observed at the current dose level, and the number of patients enrolled who are at risk of developing a DLT.

The first patient in all cohorts will be treated for 7 days taken from Day 1, before the second and third patients can take their first dose of CCT3833 in parallel. Patients who receive less than 75 % of their planned doses in Cycle 1, taken from Day 1 onwards, for reasons other than toxicity will not be evaluable for assessment of DLT for dose review decisions and will be replaced in the cohort.

In order to make the decision to escalate the CCT3833 dose, three evaluable patients must have completed one cycle of treatment (28 days). The time between cohorts is therefore approximately 6 weeks.

The dose increases between cohorts will be up to 100%, i.e. doubling of the dose (dosed on a flat scale and not by body weight or body surface area), until a probable or highly probable drug-related CTCAE v4.03 (Appendix 4) Grade 3 AE (or grade 4 haematological toxicity) is reported. Subsequent dose increases between cohorts will be driven by reported safety data and available PK and PD data. The available PK data for all patients will be reviewed as part of the dose escalation data. PK data for a minimum of two patients in the current cohort will be required to inform dose review decisions. PK data for a minimum of two patients from the previous cohort will also be required.

6.7 Communication between trial sites

Effective communication of emerging safety data and precise coordination of patient recruitment and dose allocation is imperative for the safe and smooth conduct of this trial.

6.7.1 Trial management group

Part A will be conducted in two of the largest and most experienced Phase 1 clinical trial units in the UK that are not only well experienced in the running of first-in-human oncology studies, but also have significant collaborative history with each other on such trials. The units are therefore well used to the scientific rigour required in running such early phase trials, as well as the practicalities of effective cross-site communication. In this regard, regular (usually fortnightly) operational teleconferences will be convened between the PIs (and /or delegates) of both sites and the RM-CTU, to review patient recruitment and emerging toxicity (or other) data. This is the trial management group. If more frequent communication is required, further teleconferences (in addition to the routinely scheduled teleconferences) will be arranged.

